#### **5.4.8.2. Analysis Methods**

- The improvement from baseline in SCORAD total score at Week 16 will be compared between each of the bermekimab groups and the placebo group using a MMRM.
- The improvement from baseline in BSA total score at Week 16 will be compared between each of the bermekimab groups and the placebo group using a MMRM.
- The improvement from baseline in SCORAD total scores will be summarized by treatment group over time.
- The improvement from baseline in SCORAD component scores (extent, severity, and subjective symptoms) will be summarized by treatment group at Week 16.
- The improvement from baseline in BSA will be summarized by treatment group over time.

#### **5.4.9. Global Individual Signs Score (GISS)**

##### **5.4.9.1. Definition**

Individual components of the AD lesions (erythema, infiltration/papulation, excoriations, and lichenification) are rated globally (ie, each assessed for the whole body, not by anatomical region) on a 4-point scale (from 0=none to 3=severe) using the EASI severity grading criteria. The cumulative score, which ranges from 0 to 12, is the sum of the four components. A higher score indicates more severe disease.

##### **5.4.9.2. Analysis Methods**

- The improvement from baseline in GISS total score at Week 16 will be compared between each of the bermekimab groups and the placebo group using a MMRM.

- The improvement from baseline in GISS total score will be summarized by treatment group over time.
- The improvement from baseline in GISS component score (erythema, infiltration/papulation, excoriations, and lichenification) will be summarized by treatment group at Week 16.

## 6. SAFETY

Safety will be assessed by summarizing the incidence and type of AEs and examining changes in laboratory parameters (hematology and chemistry), and vital signs data.

In all the safety analysis, randomized participants who received at least 1 (partial or complete) dose of study agent administration will be included. For safety analyses, participants will be analyzed according to the randomized treatment groups they were assigned to, regardless of the treatments they actually received. No formal statistical comparison is planned.

Depending on the safety data categories, the cumulative safety data will be analyzed through different study periods through Week 16 and Week 36. Unless otherwise specified, tabular summaries of safety events for key study periods are in general presented as following:

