### **10.3 ANALYSIS SETS**

- The safety analysis set (SAF) population will consist of all patients who receive at least one dose of study medication and will be analyzed as treated.
- The modified intent-to-treat (mITT) population will consist of all randomized and treated patients.

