### **10.5.2 Safety Analysis**

The primary objective of the study is to analyze the safety and efficacy of different dose regimens of bermekimab compared to placebo treatment in adult patients with moderate-to-severe AD

Safety endpoints will be evaluated by monitoring adverse events from clinical and laboratory reporting. The safety analysis will be based on the SAF population. A summary of safety results will be presented for each treatment group.

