## 4.3. Treatment Compliance

Study agent compliance will be summarized descriptively through Week 16 and through the end of the study (Week 36) for the FAS. Number of the participants receiving each scheduled treatment will be summarized. In addition, treatment compliance will also be assessed by protocol deviations related to study agent administration (i.e., incorrect study agent or dose received).

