### **Summaries through Week 36**

Safety data through Week 36 will be summarized by treatment groups including

1. Placebo → bermekimab qw
2. Bermekimab q2w
3. Bermekimab qw
4. Combined Bermekimab

This allows safety comparisons between each bermekimab regimen through Week 36 based on the similar follow-up time in each group.

The list of actual treatment groups for safety analyses and inclusions of participants and safety events/measurements in each group are defined as follows:

1. **Placebo:** all participants who were randomized to placebo and received treatment with placebo only or received treatment with placebo prior to receiving treatment with bermekimab. For participants who started treatment with placebo but later received bermekimab, the safety events/measurements on and after the first dose of bermekimab will be excluded from this group. Only the safety events/measurements that occurred while the participants had been receiving placebo only will be included in this group.
2. **Placebo → bermekimab 400 mg qw:** all participants who were randomized to placebo started treatment with placebo only and later received treatment with bermekimab qw. Only the safety events/measurements from these participants that occurred on and after their first administration of bermekimab will be included in this group.
3. **Bermekimab 400 mg qw:** all participants who were randomized to bermekimab qw and received bermekimab qw. All the safety events/measurements from these participants that occurred on and after their first administration of bermekimab will be included in this group.
4. **Bermekimab 400 mg q2w:** all participants who were randomized to bermekimab q2w and received bermekimab q2w. All the safety events/measurements from these participants that occurred on and after their first administration of bermekimab will be included in this group.

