### 7.1. Pharmacokinetics

All PK analyses will be based on the PK analysis set (Section 2.4.3). Participants will be analyzed according to the randomized treatment groups they were assigned to, regardless of the treatments they actually received. Unless otherwise specified, tabular summaries of PK for key study periods are in general presented as following:

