#### 7.1.1.1. Data Handling Rules

Unless otherwise specified, the following data handling rules will apply to PK analyses:

- Participants will be analyzed according to the treatment groups that they actually received.
- All concentration summaries for a particular timepoint will include data obtained from treated participants at the timepoint of interest without imputing any missing data.
- A concentration not quantifiable (below the lower limit of quantification) will be treated as 0 in the summary statistics and shown as the lower limit of quantification (< LLOQ) in the data listings.
- The data from a subject who meets 1 of the following dosing deviation criteria (if applicable) will be excluded from the by-visit data analyses from that point onwards:
  - Discontinue bermekimab administrations.
  - Skipped a bermekimab administration.
  - Received an incomplete/ incorrect dose (if applicable).
  - Received an incorrect study agent (if applicable).
  - Received an additional bermekimab dose.

In addition, if a subject has an administration outside of dosing windows (Table 2), the concentration data collected at and after that visit will be excluded from the by-visit data analyses. Additional exclusions for incongruous PK data to be implemented based on Janssen SOP-07948. All participants and samples excluded from the analysis will be clearly documented in the Clinical Study Report.

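### The SAP analyses safety by randomised arm although the protocol requires as-treated analysis, and its own safety columns leave some mis-dosed participants without a place

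*SAP*

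**What the plan says.** Protocol 10.3 states that the safety analysis set "will consist of all patients who receive at least one dose of study medication and will be analyzed as treated". Protocol 10.5.2 ties the analysis to that set: "The safety analysis will be based on the SAF population".

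SAP section 6 gives the opposite grouping: "For safety analyses, participants will be analyzed according to the randomized treatment groups they were assigned to, regardless of the treatments they actually received". SAP 2.4.2 defines who belongs to the safety set but has no as-treated grouping rule.

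Under its Week 36 summaries, SAP section 6 then lists what it calls actual treatment groups. The Placebo group leaves out anything on or after a first bermekimab dose. The Placebo → bermekimab qw group takes placebo-randomised participants who started on placebo only and later received bermekimab qw, counted from their first bermekimab dose. The weekly group is "all participants who were randomized to bermekimab qw and received bermekimab qw", and the q2w group has the same double condition. The Week 16 tables have columns for Placebo, q2w, qw and Combined Bermekimab. The Week 36 tables replace Placebo with Placebo → bermekimab qw. Combined Bermekimab is not defined for safety.

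Dosing errors are foreseen. SAP 4.3 assesses compliance through deviations such as "incorrect study agent or dose received", and SAP 4.5 lists wrong treatment or dose as a major deviation.

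**The concern.** A safety table should show what happened to people exposed to the drug. If an exposed participant's events sit under Placebo, the placebo rate rises, the bermekimab rate is understated, and an excess due to the drug is harder to see.

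The change from the protocol is also silent. SAP 5.2.1 explains openly that it departs from the protocol's multiplicity rule, but nothing comparable is said about safety, and the Amendment 1 summary mentions only Fisher's exact test. Within the SAP, the general rule and the column definitions give different answers for the same participant, so a programmer cannot follow both.

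Safety is part of the primary objective (Protocol 10.5.2, SAP 1.1), and SAP section 6 presents the Week 16 tables as the basis for comparing bermekimab with placebo.

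**Working it through.** The plan states no figure on this point, so the check is a comparison of rules followed by an illustration.

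**Step 1: where do the events go?** Each type of dosing error is passed through the general rule and the column definitions of SAP section 6. For placebo-randomised participants, the events are those after the erroneous bermekimab dose.

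| Case | General rule, Week 16 table | Column definitions, Week 16 table | Column definitions, Week 36 table |
|---|---|---|---|
| (a) Randomised to placebo, bermekimab from Week 0 | Placebo | none | none |
| (b) Randomised to placebo, wrong dose in Weeks 1 to 15, stops before receiving bermekimab qw | Placebo | none | none |
| (c) As (b), but crosses over at Week 16 | Placebo | none | Placebo → bermekimab qw |
| (d) Randomised to one active regimen, given wholly the other or only placebo | randomised arm | none | none |

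The entries of none take Combined Bermekimab to be qw plus q2w, as SAP 5.2.3 defines the combined column for efficacy.

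**Step 2: how much can it matter?** About 90 participants at 1:1:1 (SAP 1.2) give about 30 per arm. Suppose *k* placebo-randomised participants are treated as weekly bermekimab from Week 0 and each has the event, and *e* other participants in each arm have it. Both *k* and *e* are assumptions.

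- By randomised arm: placebo (e + k)/30, weekly e/30, difference (weekly minus placebo) −k/30.
- As treated: placebo e/(30 − k), weekly (e + k)/(30 + k).

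For k = 1 and e = 2:

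- By randomised arm: 3/30 = 10.0% against 2/30 = 6.7%, difference −3.3 points.
- As treated: 2/29 = 6.9% against 3/31 = 9.7%, difference +2.8 points.
- The choice of rule moves the difference by about 6.1 points and changes its sign.

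For k from 1 to 3 and e from 1 to 4, the difference by randomised arm runs from −3.3 to −10.0 points. The as-treated difference runs from +2.3 (5/31 − 4/29) to +8.4 points (4/33 − 1/27). With k = 0 the two rules agree.

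**Step 3: opportunity for error.** Up to Week 15 each participant has 2 injections at Week 0 and 15 weekly ones, 17 in all. The placebo arm therefore has about 30 × 17 = 510 injections in which bermekimab could be given by mistake. This counts opportunities and is not a rate. The protocol's COVID-19 appendix also allows home and self-administration.

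**Step 4: pharmacokinetics.** SAP 7.1 says "Participants will be analyzed according to the randomized treatment groups they were assigned to, regardless of the treatments they actually received", while SAP 7.1.1.1 says "Participants will be analyzed according to the treatment groups that they actually received". The wording conflicts. However, 7.1.1.1 also removes by-visit data from the point of an incorrect agent or dose, an extra bermekimab dose or a skipped one.

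**The case against.** The strongest reply is that the specific column definitions override the general sentence. On that reading the Placebo column is not contaminated, because events from the first bermekimab dose are taken out of it. This is fair, but those events then have no column in the Week 16 tables, and the protocol's rule is still not applied.

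Four stronger readings are tempting, and the documents do not support them.

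- *The events vanish from every column.* In case (c) they appear in the Week 36 tables. A weekly participant given a few stray placebo syringes can also still be read as having received the weekly regimen; only a wholly different regimen clearly falls outside the definitions.
- *The events are lost from the report.* SAP 6.1 includes all reported treatment-emergent events and lists participants with serious events, events of grade 3 or higher, events leading to discontinuation, and anaphylactic or serum sickness-like reactions. Major deviations are listed too. The issue is placement in the summary tables.
- *The bias always runs towards no difference.* The illustration crosses zero. What can be said is that counting exposed participants' events under placebo works against detecting a drug-related excess.
- *Drug levels are attributed to the wrong regimen.* The exclusions in SAP 7.1.1.1 largely prevent this in the by-visit summaries, so only a conflict of wording remains.

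It is also true that no formal safety test is planned and that nothing changes unless dosing errors occur. Neither removes the contradiction, since the tables are meant for between-group comparison.

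**Conclusion.** The point holds. The SAP replaces the protocol's as-treated rule with a randomised-arm rule without declaring it, and its column definitions cannot be reconciled with that rule. For the Week 16 tables, events after erroneous bermekimab in a placebo participant fall under Placebo or in no defined column. For the Week 36 tables, they appear only for those who started on placebo and later received bermekimab qw.

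The contradiction is certain from the text; the numerical effect is conditional. The documents give no dosing-error rate, and the shift of about 6 points for one participant assumes 30 per arm, that this participant has the event, and two other events per arm. At this sample size a single misplacement can reverse the apparent direction for an uncommon event, so the wording deserves correction.

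**What to change.** - In SAP section 6, replace the randomised-arm sentence with the protocol's rule: safety is analysed according to the treatment actually received.
- In the column definitions, remove the double condition of being both randomised to and given a regimen, so that every treated participant and event falls in exactly one regimen column per table.
- In the Week 16 tables as well, count events on and after a first bermekimab dose in a placebo-randomised participant as bermekimab-exposed, in a named column that feeds Combined Bermekimab. Define Combined Bermekimab for safety.
- State one rule for assigning mixed exposure, under which the planned placebo injections in the q2w arm count as q2w.
- Bring SAP 7.1 into line with SAP 7.1.1.1, for consistency only.
- Leave efficacy by randomised arm.

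The cost is SAP wording and one derived actual-treatment variable. Safety and efficacy denominators may differ slightly.

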### **Summaries through Week 16 (placebo controlled):**

Safety data through Week 16 will be summarized by treatment groups

1. Placebo
2. Bermekimab q2w
3. Bermekimab qw
4. Combined Bermekimab

This allows between-group comparisons of safety between the bermekimab regimens and the placebo group based on similar follow-up period in each group.

### **Summaries through Week 36**

Safety data through Week 36 will be summarized by treatment groups including

1. Placebo → bermekimab qw
2. Bermekimab q2w
3. Bermekimab qw
4. Combined Bermekimab

This allows safety comparisons between each bermekimab regimen through Week 36 based on the similar follow-up time in each group.

The list of actual treatment groups for safety analyses and inclusions of participants and safety events/measurements in each group are defined as follows:

1. **Placebo:** all participants who were randomized to placebo and received treatment with placebo only or received treatment with placebo prior to receiving treatment with bermekimab. For participants who started treatment with placebo but later received bermekimab, the safety events/measurements on and after the first dose of bermekimab will be excluded from this group. Only the safety events/measurements that occurred while the participants had been receiving placebo only will be included in this group.
2. **Placebo → bermekimab 400 mg qw:** all participants who were randomized to placebo started treatment with placebo only and later received treatment with bermekimab qw. Only the safety events/measurements from these participants that occurred on and after their first administration of bermekimab will be included in this group.
3. **Bermekimab 400 mg qw:** all participants who were randomized to bermekimab qw and received bermekimab qw. All the safety events/measurements from these participants that occurred on and after their first administration of bermekimab will be included in this group.
4. **Bermekimab 400 mg q2w:** all participants who were randomized to bermekimab q2w and received bermekimab q2w. All the safety events/measurements from these participants that occurred on and after their first administration of bermekimab will be included in this group.

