 Assessments/procedures should be conducted in the following order: patient reported outcomes, investigator assessments, safety and laboratory assignments, administration of the study drug.																		
 Concomitant medications within 30 days before screening until 7 days after the last administration of the study drug must be recorded for the purpose of drug-drug and drug-disease interaction evaluation and signal detection																		
 Loading Doses: Treatment arm 1: 800 mg loading dose of bermekimab + placebo (one 2mL SC injection containing 400 mg of bermekimab and one 2mL SC injection of placebo) at week 0; Treatment arm 2: 800 mg loading dose of bermekimab (2 x 2mL SC injections each containing 400 mg of bermekimab) at week 0; Arm 3: 4 mL loading dose of placebo (2 x 2mL SC injections of placebo) at week 0.																		
 Patients in Arm 3 will begin to receive active bermekimab therapy at visit 17 (week 16). Patients in all arms will remain blinded through end of study.																		

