## **7. ASSESSMENT OF SAFETY**

Safety will be assessed by monitoring adverse events, vital signs, physical examinations, ECG, and clinical laboratory measurements. Data from ECG will be included in safety analysis only when all of these measures are available for each subject (baseline and last visit). Adverse events will be monitored from visit 1 (post-injection) through visit 34 (week 36). Any serious adverse events whether related to study drug or not will be followed up until resolution.

Study drug, bermekimab, will be administered under close observation in a facility equipped to handle anaphylaxis or injection site reactions. Subjects must be closely monitored at the study site at visits 1, 2 and 3 (for the first three injections) until at least 30 minutes following the administration of the antibody. Vital signs and AE assessments will be done at 30 minutes (+/- 10 minutes) post-injection.

Any grade 3 or greater injection site reaction must be reported to the sponsor within 24 hours of learning of the event.

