### 1.2. Trial Design

This is a phase II, randomized, double-blind, placebo-controlled study to further establish the efficacy, safety, PK, and explore dose effects for bermekimab monotherapy in adults with moderate to severe Atopic Dermatitis (AD). The participant population will comprise men and women who have had chronic atopic dermatitis present for at least 3 years. The study is approximately 40 weeks (30 day screening period, 32-week treatment period and a 4-week follow-up period) for all subjects.

A diagram of the study design ([Figure 1](#)) is provided below, approximately 90 patients who meet the eligibility criteria at screening will be randomized in a 1:1:1 ratio to one of two active treatment arms or placebo:

- Arm 1: 400 mg loading dose of bermekimab (2mL SC injection containing 400 mg of bermekimab and one 2mL SC injection of placebo) at Week 0 followed by weekly (qw) subcutaneous (SC) injections of 400 mg bermekimab through Week 31
- Arm 2: 800 mg loading dose of bermekimab (2 x 400 mg SC injections) at Week 0 followed by subcutaneous (SC) injections of 400 mg bermekimab every other week (q2w) alternating with matching placebo q2w through Week 31.

- Arm 3: 4mL loading dose of placebo (2 x 2mL SC injections) at Week 0 followed by weekly placebo injections from Week 1 through Week 15. Patients in Arm 3 will begin to receive weekly (qw) blinded subcutaneous (SC) injections of 400 mg bermekimab beginning at Week 16 through Week 31.

Patients will be monitored at a follow up visit (week 36) for safety and clinical assessments after completing the 32 week treatment period.

Efficacy assessments include Eczema Area and Severity Index Score (EASI) score, Itch Numerical Rating Scale (NRS), Pain NRS, Severity Scoring of Atopic Dermatitis (SCORAD), Patient Oriented Eczema Measure (POEM), Global Individual Signs Score (GISS), Dermatology Life Quality Index (DLQI), Hospital Anxiety Depression Scale (HADS), Body Surface Area (BSA) and Investigator's Global Assessment (IGA) will be performed according to the Study Calendars (Section 5.2 of the protocol).

Blood samples will be collected for laboratory testing including chemistry, hematology, inflammation markers, bermekimab concentration (PK), PD marker(s), and anti-drug antibody (ADA).

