## 4.4. Extent of Exposure

The exposure data will be summarized through Week 16 and Week 36. The number and percentage of participants who receive study agent will be summarized by treatment group for the safety analysis set. Descriptive statistics will be presented for the following parameters:

- Number of administrations
- Cumulative total dose

In addition, the average exposure (number of administrations) and average duration of follow-up (weeks) will also be summarized by treatment group in the safety tables through different study time periods.

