### 6.1. Adverse Events

The verbatim terms used in the CRF by investigators to identify adverse events will be coded using the Medical Dictionary for Regulatory Activities (MedDRA). Any AE starting at or after the initial administration of study agent through the end of the trial is considered as treatment emergent. If the event occurs on the day of the initial administration of study agent, and either event time or time of administration are missing, then the event will be assumed to be treatment emergent. If the event date is recorded as partial or completely missing, then the event will be considered as treatment emergent unless it is known to be prior to the first administration of study agent based on partial onset date or resolution date. All reported treatment-emergent adverse events will be included in the analysis.

The following analyses will be used to assess the safety of participants in the study:

- The incidence and type of AEs.
- The incidence and type of SAEs.
- AEs of severe intensity
- AEs leading to discontinuation of study
- The incidence and type of reasonably related AEs.

These summary tables will provide the count and percentage of participants with 1 or more of the specified AEs by treatment group. In addition to the summary tables, listings will be provided for participants who:

- Had SAEs
- Had AEs leading to discontinuation of study
- Had AEs of severe or life threatening, or fatal based on CTCAE (grade $\geq$ 3) intensity
- Had anaphylactic or serum sickness-like reactions.

Since safety should be assessed relative to exposure and follow-up, most AE summary tables will include average weeks of follow-up and average number of study agent administrations, and injections for each treatment group.

In addition, a participant who had injection site reaction(s) in 30 minutes (+/- 10) post injection at Weeks 0, 1, and 2 were recorded in eCRF. The incidence of injection-site reaction during this time frame will be summarized.

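### The SAP says follow-up is similar across the Week 36 safety columns, but the placebo-to-bermekimab column covers about 20 weeks against 36 for the other two regimens

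*SAP*

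**What the plan says.** SAP section 6, under Summaries through Week 36, lists four columns: placebo then bermekimab qw, bermekimab q2w, bermekimab qw, and combined bermekimab. Directly below the list it says: "This allows safety comparisons between each bermekimab regimen through Week 36 based on the similar follow-up time in each group".

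The same subsection then defines the columns. For participants who cross over from placebo: "Only the safety events/measurements from these participants that occurred on and after their first administration of bermekimab will be included in this group". The qw and q2w columns also count from first bermekimab dose, which for them is Week 0.

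SAP 1.2 gives the placebo arm "injections of 400 mg bermekimab beginning at Week 16 through Week 31". Footnote 7 of the calendar in Protocol 5.2.1 also puts the start of active treatment at Week 16. Protocol 7 ends AE monitoring at the Week 36 visit.

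On presentation, SAP 6.1 says: "These summary tables will provide the count and percentage of participants with 1 or more of the specified AEs by treatment group". It adds: "Since safety should be assessed relative to exposure and follow-up, most AE summary tables will include average weeks of follow-up", together with the average number of administrations. SAP 4.4 likewise says that "average duration of follow-up (weeks) will also be summarized by treatment group in the safety tables". SAP 6.2 summarises the worst CTCAE laboratory grade by treatment group. SAP section 6 states that no formal safety comparison is planned.

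**The concern.** The percentage of participants with at least one event depends on how long they are observed. A column that observes people for just over half as long will tend to show a lower percentage, even if the underlying risk is identical. The SAP places such a column beside two full-length columns and describes follow-up as similar.

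Safety is part of the primary objective (SAP 1.1). The crossover column is also a natural place to look at weekly dosing without the Week 0 start. A reader who trusts the sentence could take a lower AE percentage there as reassurance about the drug, when shorter observation alone could produce it.

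**Working it through.** **Inputs.** Week 0 is Day 0, Week 16 is Day 112 and Week 36 is Day 252 (Protocol 5.2 calendars). Visit windows are ±3 days (SAP 2.2). Weekly injections run through Week 31 (SAP 1.2). The SAP attaches no number to its statement, so there is no figure to reproduce.

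**Follow-up counted, for completers.** Follow-up = (252 − day of first counted bermekimab dose) / 7.
- qw and q2w: (252 − 0)/7 = 36 weeks each. The statement is correct for this pair.
- Placebo then qw: (252 − 112)/7 = 20 weeks. With ±3 days at both ends, (140 ± 6)/7 gives 19.1 to 20.9 weeks.
- Ratio: 20/36 = 0.56.
- In the Week 16 tables every column covers 16 weeks, so the parallel statement there is correct.

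**Nominal dosing visits.** Weeks 0 to 31 give 32; Weeks 16 to 31 give 16. For q2w, injections alternate between active drug and placebo, so visits are not active doses.

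**Effect on percentages (illustration only).** The documents give no expected AE rates for this trial, so the 36-week incidence p36 is assumed over a range. With the same risk in every column, the 20-week incidence is p20 = 1 − (1 − p36)^((20/36)^k). Here k = 1 is a constant rate and k = 0.5 is early clustering (Weibull shape). Example at k = 1: 1 − 0.60^(0.556) = 0.247.

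| 36-week incidence | Seen at 20 weeks, k = 1 | Seen at 20 weeks, k = 0.5 | Gap at k = 1, in participants, if 30 per arm |
|---|---|---|---|
| 60% | 39.9% | 49.5% | 6.0 |
| 40% | 24.7% | 31.7% | 4.6 |
| 20% | 11.7% | 15.3% | 2.5 |
| 10% | 5.7% | 7.6% | 1.3 |
| 3% | 1.7% | 2.2% | 0.4 |

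If every first event fell within 20 weeks of starting bermekimab, there would be no gap.

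**Laboratory samples.** The visit descriptions in Protocol 5.2 schedule chemistry and haematology after baseline at Weeks 4, 8, 12, 16, 24, 32 and 36. That is 7 samples after first dose for qw and q2w. The crossover group's Week 16 sample is drawn before its first bermekimab injection, leaving Weeks 24, 32 and 36, which is 3 samples. If the counting rule were applied by calendar date, the same-day Week 0 and Week 16 draws would be added, giving 8 and 4. A worst-of-n summary tends to rise with n. If each sample independently had a 5% chance of grade 2 or more (assumed), 1 − 0.95^7 = 30% against 1 − 0.95^3 = 14% of participants would show it. Correlation within a participant shrinks that contrast, to nothing if perfect.

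**The case against.** The strongest reply is that the sentence is about bermekimab regimens. SAP 5.1 uses that language for qw and q2w, and for those two it is true. But the sentence speaks of the follow-up in each group, and it sits directly under a list whose first entry is the crossover column. The narrow reading is possible, but the text does not say it.

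Second, the gap is disclosed. The column definition is explicit, and average follow-up and administrations will be printed in most AE tables. This stands: a reader might infer that the imbalance is hidden, and it is not. Disclosure does not make the statement true, however, and it does not put the percentages on a common footing.

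Third, the consequence rests on assumed rates in a descriptive section. This also stands. The documents do not support a claim of a known bias: the gap could be zero if first events come early, and for uncommon events it is under one or two participants in an assumed 30 per arm.

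Two further inferences are tempting. One is that the worst-grade laboratory table is certainly distorted. SAP 6.2 names neither a period nor columns for it, and the counts above are scheduled samples only, so that point is conditional. The other is that the safety comparison as a whole is unsound. It is not: the randomised qw against q2w comparison and the placebo-controlled Week 16 tables have matched follow-up.

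**Conclusion.** The statement is wrong as written for one of the listed columns. The crossover column covers about 20 scheduled weeks and 16 nominal dosing visits, against 36 weeks and 32 visits. These figures follow from the documents alone and assume completion; dropout would shorten follow-up in every column.

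The direction of the effect on crude AE percentages is clear unless first events cluster early: the crossover column will tend to look lower. The size is unknown. If worst laboratory grade is tabulated over the same Week 36 columns, it would rest on 3 scheduled samples against 7.

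This should be corrected, but its reach is limited. The primary efficacy analysis is not affected, and no formal safety test depends on it.

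**What to change.** 1. Limit the similar-follow-up statement to qw against q2w, and state that the placebo-to-bermekimab column covers about 20 weeks from Week 16.
2. Keep every planned Week 36 table. Add a descriptive summary of AEs, SAEs and AEs leading to discontinuation over the first 16 weeks from first bermekimab dose: Weeks 0 to 16 for qw and q2w, Weeks 16 to 32 for crossover. The Week 16 tables already plan the qw and q2w columns, so the new element is mainly one crossover column. Footnote that the comparison with crossover is not randomised; that it is limited to placebo participants who stayed to receive bermekimab; that it omits Weeks 32 to 36; and that it is matched on nominal visits, not on active doses for q2w. The match of 16 dosing visits is itself only nominal, because visit windows could place a Week 16 injection inside 112 days for qw and q2w, while the crossover group has none at Week 32.
3. State the period and columns for the worst-laboratory-grade table. Keep it in full and show the number of samples per group. A table using only the samples 8 and 16 weeks after first bermekimab dose (Weeks 8 and 16; Weeks 24 and 32) may supplement it but must not replace it, since it could miss a true worst value.
4. Rates per 100 patient-years are optional. They assume a roughly constant rate. With early clustering (k = 0.5) and identical risk, first events per patient-year at risk would come out 1.28 to 1.34 times higher in the crossover column.

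Two separate minor clarifications add nothing to the weight of this point. The safety section should say whether its combined Week 36 column includes crossover participants, as SAP 5.2.3 does for efficacy. The as-treated wording in Protocol 10.3 should also be reconciled with the as-randomised wording in SAP section 6.

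The cost is a sentence, footnotes and a few tables from data already collected. There is no operational change. The price is more output, and a matched window that uses 16 of the crossover group's 20 weeks.
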